### **6.5 Anesthesia protocol for both intervention and control group**

- 1) During the study period (from preop to postop day 5), anticholinergics such as scopolamine are strictly prohibited; atropine or glycopyrrolate can only be used for treatment of bradycardia; the use of midazolam for anxiolysis is allowed but not encouraged;
- 2) In both arms, the anesthesia induction is per standard care using agents of lidocaine, propofol, sufentanyl and muscle relaxant. The administration of propofol in the intervention arm is via pump infusion and guided by SedLine.
- 3) The anesthesia is maintained using propofol infusion (0-200 mcg/kg/min) and remifentanyl infusion (0.05-0.2 mcg/min/kg). Sufentanyl and muscle relaxant boluses can be used during surgery.
- 4) The anesthetic adjustment in the control arm is per the conventional practice (EEG monitored but blinded to anesthesia team) and in the intervention arm per the **Supplemental remark 1. SedLine-Guided Intervention Flow Chart**.

## **7. Data collection**

### **7.1 Preoperative data**

- 1) Determine patient's eligibility based on the inclusion and exclusion criteria;
- 2) Mini-mental Status Exam;
- 3) Demographic data, past medical and surgical history, medications taken at home and in hospital;
- 4) Electrocardiogram, echocardiogram if available;
- 5) Lab results.

## 7.2 Intraoperative data

- 1) Surgical details including type and time of surgery;
- 2) Anesthetic details including the name and dose of any drugs used during surgery;
- 3) The total dose of propofol used for anesthesia induction and maintenance;
- 4) Inputs and outputs including the name and volume of the fluid being administered, the estimated blood loss, the urine output, and any blood products being transfused;
- 5) EEG data including the occurrence, duration and percentage of burst-suppression, SEF and PSI (specific to SedLine monitor).

## 7.3 Postoperative data

- 1) PACU Delirium: Occurrence of delirium in PACU will be assessed using the CAM-ICU 30 mins after extubation and before PACU discharge.
- 2) Postoperative Delirium (POD): POD will be assessed twice daily (8:00-10:00 am, and 18:00-20:00 pm) for 5 days from postoperative day 1 to 5 or until the patient is discharged home if the patient stays in hospital < 5 days. CAM is used for delirium assessment if the patient is on the floor; otherwise, CAM-ICU is used if the patient is in the ICU. Investigators for POD assessment will be trained by a psychiatrist to use CAM and CAM-ICU before the trial is commenced.
- 3) Non-delirium Complications: Any complications occurred within the first 30 days after surgery (for example: cardiac events, cerebrovascular events, renal injury, GI complications, infections, etc.) will be documented. Patients will be assessed via phone call if they are discharged before day 30 after surgery.
- 4) Subjective Pain Score: It will be assessed at PACU and 24 hours after surgery using the Numeric Rating Scale (NRS) (an 11-point scale where 0 indicates no pain and 10 indicates the worst pain).
- 5) Subjective Sleep Quality: It will be assessed at 8:00 am during the first postoperative day using the NRS (an 11-point scale where 0 indicates the best possible sleep and 10 indicates the worst possible sleep).
- 6) Length of Hospital Stay: The readiness for discharge will be used as the last day of hospitalization.
- 7) All-cause 30-day Mortality: Patients or family members will be called for assessment.
- 8) Adverse Events: If an adverse event occurs during patient hospitalization, it will be followed up until its disappearance or therapy ends.

## 8. Outcome

### 8.1 Primary outcome

Incidence of postoperative delirium during the first 5 days after surgery.

## 8.2 Secondary outcomes

The secondary outcomes are as follows:

- 1) Incidence of emergence delirium;
- 2) Composite complication classified as Clavien-Dindo grade II or greater within postoperative 30 days;
- 3) 24-hour postoperative nausea and vomiting (PONV);
- 4) MMSE score change;
- 5) Length of hospital stay;
- 6) Intensive care unit (ICU) admission;
- 7) 30-day hospital readmission;
- 8) 30-day all-cause mortality

Postoperative complications are as follows:

- Myocardial ischemia or infarction
- Arrhythmia requiring treatment
- Circulatory insufficiency (requiring a vasopressor or inotropic agent infusion for more than 6 hours)
- Ischemic stroke
- Hemorrhagic stroke
- Acute lung injury
- Pulmonary embolism
- Pulmonary infection requiring antibiotic treatment
- Hypoxemia or respiratory insufficiency requiring supportive treatment including intubation, CPAP, BiPAP, high-flow (>10 L/min) face mask or nasal cannula for more than 6 hours
- Acute kidney injury requiring treatment
- Urinary tract infection requiring antibiotic treatment
- Ileus
- Sepsis
- Anastomotic leakage requiring treatment
- Urinary retention requiring treatment
- Pleural or intra-abdominal effusion requiring intervention
- Wound dehiscence requiring intervention
- Bowel obstruction requiring treatment
- Deep venous thrombosis requiring treatment
- Subcutaneous emphysema requiring treatment
- Surgical bleeding or hematoma requiring intervention
- Surgical site infection (superficial or deep, but not organ or space) requiring antibiotic treatment or procedural treatment (not at bedside)
- Surgical site infection (pelvic or intra-abdominal infection or abscess, i.e., organ or space) requiring antibiotic treatment or procedural treatment (not at bedside)

- Delayed emergence requiring treatment

The Clavien-Dindo Classification (<https://www.assessurgery.com/clavien-dindo-classification/>)

Grades	Definition
Grade I	Any deviation from the normal postoperative course without the need for pharmacological treatment or surgical, endoscopic and radiological interventions Allowed therapeutic regimens are: drugs as antiemetics, antipyretics, analgetics, diuretics and electrolytes and physiotherapy. This grade also includes wound infections opened at the bedside.
Grade II	Requiring pharmacological treatment with drugs other than such allowed for grade I complications. Blood transfusions and total parenteral nutrition are also included.
Grade III	Requiring surgical, endoscopic or radiological intervention
- IIIa	Intervention not under general anesthesia
- IIIb	Intervention under general anesthesia
Grade IV	Life-threatening complication (including CNS complications)* requiring IC/ICU-management
- IVa	single organ dysfunction (including dialysis)
- IVb	Multiorgan dysfunction
Grade V	Death of a patient

\*brain hemorrhage, ischemic stroke, subarachnoidal bleeding, but excluding transient ischemic attacks (TIA); IC: Intermediate care; ICU: Intensive care unit.

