### 8.3 Additional outcomes

- 1) NRS pain score at PACU and 24 hours after surgery;
- 2) NRS score of subjective sleep quality at 8:00 am of postoperative day 1.

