## **13. Statistical analysis**

### **13.1 General principles**

- 1) Numeric variables will be presented as mean (standard deviation) or median (minimum, maximum; or interquartile range). Categorical variables will be presented as number of cases (percentage);
- 2) Two-tailed tests will be used in all statistical analysis, and a p value of less than 0.05 will be considered to be of statistical significance for the primary outcome. The Benjamini-Hochberge procedure will be applied to control for the multiple testing for all secondary outcomes.

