## Flow chart of the study

	Screen	Recruitment	Intraoperative	Postoperative follow-up								
				PACU	D1	D2	D3	D4	D5	D6-discharge	D30±3	
Inclusion/exclusion criteria	X	X										
Informed consent	X											
Demographic data	X	X										
Preoperative diagnosis	X	X										
Previous medical history	X	X										
Physical examination	X	X										
Auxiliary examination	X	X										
MMSE	X	X										
Baseline CAM	X	X										
Anesthesia			X									
Study protocol execution		X	X	X	X	X	X	X	X	X	X	X
Delirium assessment*				X	X	X	X	X	X			
Adverse events				X	X	X	X	X	X	X		
NRS of severity of pain				X	X							
NRS of subjective sleep quality					X							
Use of other drugs				X	X	X	X	X	X	X		
Postoperative complications**				X	X	X	X	X	X	X		X
All-cause 30-day mortality												X

\*Delirium will be assessed at PACU and twice daily (8:00-10:00 am and 18:00-20:00 pm) during postoperative day 1 to 5.

\*\*Patients will be followed up until postoperative day 30.

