**Record of adverse events**

An adverse event indicates any unpredictable, unfavorable medical event that is associated with any medical intervention and occurs during the study period. It can be related to the study or not.

A severe adverse event indicates any unpredictable medical events that lead to death, threat to life, prolonged length of stay in hospital, persistent disability or dysfunction, or other severe results.

Any adverse event should be followed up until it is completely resolved or therapy terminated.

**Is there any new adverse event within 24 hours after surgery:** Yes; No

**Is there any new severe adverse event within 3 days after surgery:** Yes; No

(Report form of severe adverse event see attached table)

	Start time	End time	Diagnostic evidence	Mode of occurrence	Is it severe adverse event?	Treatment 	Outcome 	Related to study?
Recall 				 Persistent  Transient	 Yes  No			 Yes  No
Hypotension 				 Persistent  Transient	 Yes  No			 Yes  No
Bradycardia 				 Persistent  Transient	 Yes  No			 Yes  No
Hypertension 				 Persistent  Transient	 Yes  No			 Yes  No
Tachycardia 				 Persistent  Transient	 Yes  No			 Yes  No
Hypoxemia 				 Persistent  Transient	 Yes  No			 Yes  No
Other:				 Persistent  Transient	 Yes  No			 Yes  No

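### 24-hour PONV is a secondary outcome that is neither defined nor specifically elicited, so a blank record cannot separate no PONV from not asked

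*Combined protocol and SAP*

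**What the plan says.** Section 8.2, item 3, lists "24-hour postoperative nausea and vomiting (PONV" among eight secondary outcomes. It does not say whether nausea, vomiting or either counts, who asks, or when.

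Section 13.1 says the Benjamini-Hochberg procedure will be "applied to control for the multiple testing for all secondary outcomes", so a PONV p-value is required. Section 13.5 gives tests for continuous, time-to-event, complication and mortality endpoints, but does not name PONV.

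Section 7.3 has eight postoperative items, none of them PONV. The nearest is the item on non-delirium complications, whose examples are "cardiac events, cerebrovascular events, renal injury, GI complications, infections, etc". By contrast, pain, which is only an additional outcome, has an instrument and times: "It will be assessed at PACU and 24 hours after surgery using the Numeric Rating Scale (NRS".

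The visit schedule (Flow chart of the study) has rows such as "NRS of severity of pain" and "Use of other drugs", but none for PONV. The CRF page for adverse events asks "Is there any new adverse event within 24 hours after surgery" and then prints rows for recall, hypotension, bradycardia, hypertension, tachycardia, hypoxemia and blank 'Other' lines.

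**The concern.** A named secondary outcome normally has a definition, a scheduled question and a field to record the answer. Staff who complete this CRF exactly as printed produce no specific PONV data. What is recorded depends on whether someone thinks to write it down. The case definition and the data source would then have to be chosen after the fact.

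Two things are at stake. Cases are likely to be undercounted, which costs power on this outcome. The resulting p-value also enters the multiplicity family, where it helps to determine the adjusted results of the other seven outcomes.

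**Working it through.** **Step 1. Trace each secondary outcome to the place where it is collected.**

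| Section 8.2 outcome | Section 7.3 | Own row for it after surgery in the schedule | CRF or supplement |
|---|---|---|---|
| 1 Emergence delirium | yes | yes | Delirium Assessment |
| 2 Composite complications | yes | yes | Postoperative complications |
| 3 PONV | no | no | **none** |
| 4 MMSE change | no | no (preoperative marks only) | Supplemental remark 2, two score columns |
| 5 Length of stay | yes | no | Hospital discharge information |
| 6 ICU admission | no | no | Postoperative page |
| 7 30-day readmission | no | no | Hospital discharge information |
| 8 30-day mortality | yes | yes | Hospital discharge information |

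Four outcomes are missing from 7.3 and five have no row of their own after surgery. Only PONV is missing from all three places (1 of 8). The CRF column is therefore the one that carries the point.

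**Step 2. Look for indirect routes.**

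- *Adverse events.* The 24-hour question is general. Nausea and vomiting are not printed rows, and PONV is not among the predicted events in Section 9.1. Section 9.1 also defines an adverse event as something unpredictable, so staff could reasonably leave PONV out.
- *Complications.* Vomiting appears on the CRF only as a criterion for ileus, and nausea only in the ileus definition in Section D. PONV is not in the complication list of Section 8.2 or the table shell in Section G. The Clavien-Dindo table puts antiemetics in grade I, so PONV treated only with antiemetics falls outside the grade II-or-greater composite. Blank 'Other complications' rows remain.
- *Drugs.* The schedule has a row for other drugs from PACU to discharge, but the only postoperative drug form shown is for the analgesia pump. The ondansetron and tropisetron boxes are in the intraoperative table.

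**Step 3. What a blank means.** The CRF instructions require every item to be completed and give codes for unknown and not applicable. With no PONV item there is nothing to code, so silence covers both no PONV and not asked.

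**Step 4. What this could cost.** The documents give no PONV rate, so this is illustration only. The plan's own figure comes first. For the primary outcome, p1 = 0.14, p2 = 0.14 × 2/3 = 0.0933 and mean p = 0.1167:

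n = [1.960√(2p(1−p)) + 0.8416√(p1(1−p1) + p2(1−p2))]² / (p1−p2)² = (0.8898 + 0.3811)² / 0.04667² = 741.7, which rounds up to 742 per group, as stated in Section 4.2.

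Now keep n = 742 and assume true PONV rates and a fraction c of cases recorded, equal in both arms and with no false positives:

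Power = Φ{[c·|p1−p2|·√742 − 1.960√(2p(1−p))] / √(p1(1−p1) + p2(1−p2))}, where every p under a root is multiplied by c.

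For 30% vs 24% with c = 1: (1.634 − 1.231) / 0.6264 = 0.64, so power is 74%.

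| Assumed true rates | c = 1 | c = 0.6 | c = 0.3 |
|---|---|---|---|
| 30% vs 24% | 74% | 47% | 25% |
| 30% vs 22.5% | 91% | 66% | 36% |

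These are at nominal two-sided 0.05, before the Benjamini-Hochberg step. The risk difference shrinks with c (6 points becomes 3.6 or 1.8), but the relative risk does not: 0.24c / 0.30c = 0.80 for any c.

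**Step 5. Sleep.** The additional outcome "NRS score of subjective sleep quality at 8:00 am of postoperative day 1" is described in 7.3 and scheduled for day 1, but the CRF text shows a score box for pain only.

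**The case against.** Absence from Section 7.3 and the schedule proves little, because MMSE change, ICU admission and readmission are missing from 7.3 too and still have forms. That stands. A reader might infer that 7.3 is a complete list and that omission from it settles the matter, and the documents do not support that. The point rests on the absence of a CRF field as well.

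A reader might also infer that nobody ever asks. That goes too far. Each CRF has a general question on new adverse events over the same 24-hour window, with free lines, and Section 7.3 requires any complications to be documented. Some PONV, or antiemetic use, could be written in. What remains true is that no route asks about nausea or vomiting specifically.

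Finally, under Section 5.2 the postoperative follow-up staff are blinded, which makes recording that differs by arm less likely. With equal under-recording and no false positives the relative risk is preserved, and the plan calls relative risk its measure of effect size. This stands as well: the expected harm is mainly lost power and an unclear denominator.

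**Conclusion.** The point holds in this form: PONV is a prespecified secondary outcome with no definition and no specific collection item in the text shown, and it is the only one of the eight in that position. An undercount is likely. Its size, and the power it costs, cannot be stated from the documents. The percentages in Step 4 show the mechanism under assumed rates and equal capture, and they are not estimates for this trial.

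A reader might go further and infer that an undercount would hide a harm or benefit produced by the change in propofol. The documents say only that propofol is adjusted to EEG targets in the intervention arm. They say nothing about its effect on PONV, so that inference is not supported.

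Neither the primary outcome nor the sample size is affected. Some pages of the public file (of the title, signature, contact and consent kind) could not be read, so a PONV form elsewhere cannot be wholly excluded, but Section 7.3, the schedule and the postoperative CRF pages are present. The sleep-score gap is separate and minor, because that outcome is otherwise fully specified.

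**What to change.** Define PONV in Section 8.2 as nausea or vomiting from the end of surgery to 24 hours. Add it to Section 7.3, the visit schedule and the CRF as a yes/no item, with rescue antiemetic yes/no beside it. The blinded follow-up staff should ask it at the existing 24-hour pain assessment, using the CRF's codes for unknown and not applicable where no answer can be had. Name PONV in Section 13.5 as a binary endpoint.

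If collection is already complete, keep PONV listed as prespecified and state in the SAP and the report where the data came from and that an undercount is likely. Deleting it from the secondary outcomes or the multiplicity family at that stage would invite a charge of selective reporting.

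Separately, add the sleep NRS score box for postoperative day 1.

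The cost is one or two CRF boxes at a contact that already takes place, with no extra visit or staff.

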### 8.3 Additional outcomes

- 1) NRS pain score at PACU and 24 hours after surgery;
- 2) NRS score of subjective sleep quality at 8:00 am of postoperative day 1.

## 9. Adverse events

### 9.1 Definition

- 1) An adverse event indicates any unpredictable, unfavorable medical event that is associated with any medical intervention and occurs during the study period. It can be related to the study protocol or otherwise. It can manifest as any uncomfortable signs (including abnormal laboratory findings), symptoms or transient morbidity;
- 2) Predicted adverse events in this study:
  - Tachycardia: heart rate > 100 beats per minute or, in case of a baseline value > 83 beats per minute, an increase of more than 20% from baseline;
  - Hypertension: systolic blood pressure > 160 mmHg or, in case of a baseline value > 133 mmHg, an increase of more than 20% from baseline;
  - Bradycardia: heart rate < 55 beats per minute or, in case of a baseline value < 69 beats per minute, a decrease of more than 20% from baseline (before study drug infusion);
  - Hypotension: systolic blood pressure < 95 mmHg or, in case of a baseline value < 119 mmHg, a decrease of more than 20% from baseline;

- Recall: the patient remembers the details of the event(s) that occurs during the period when the patient is under appropriate general anesthesia per standard of care.

Note: for heart rate and blood pressure, the average values measured before surgery are used as baseline values.

## **9.2 Management**

- 1) Therapy will be provided according to standard clinical practice;
- 2) The study protocol can be stopped temporarily or permanently if considered necessary by the attending anesthesiologist or the principal investigators. The time and reasons of study interruption will be recorded in CRFs.

Management of predicted adverse events in this study:

- 1) Bradycardia: administration of medication (e.g. atropine iv bolus) and/or adjustment of anesthetic agents;
- 2) Hypotension: intravenous fluid bolus, administration of medication (vasopressor iv bolus or infusion), and/or adjustment of anesthetic agents;
- 3) Tachycardia: administration of medication (esmolol or diltiazem) and/or adjustment of anesthetic agents;
- 4) Hypertension: administration of medication (labetalol or nicardipine) and/or adjustment of anesthetic agents;

## **9.3 Recording**

- 1) Any adverse event should be documented, including type, timing, duration, management, and sequelae;
- 2) Any adverse event should be followed up until it is completely resolved or the therapy is terminated.

## **10. Severe adverse events**

### **10.1 Definition**

A severe adverse event indicates any unpredictable medical events that lead to death, threat of life, prolonged length of hospital stay, persistent disability or dysfunction, or other severe event.

### **10.2 Management**

In case of any severe adverse events, the study protocol will be stopped and treatment will be initiated immediately.

### **10.3 Recording and reporting**

- 1) In case of any severe adverse event, apart from active treatment and record as above, the principal investigator and the Ethics Committee will be informed within 24 hours in written report;
- 2) In case of study drug related death, immediately stop the clinical trial, report the event to the Ethics Committee as soon as possible, record in detail and carefully preserve the related documents;
- 3) Any severe adverse event must be followed up until it is completely resolved or the therapy is terminated.

## **11. Unmask of blinding**

For an individual patient, at the completion of the study (30 days after surgery), all data are checked to ensure its quality and input into the database, the database will be locked up and the blindness will be unmasked.

## **12. Data management**

- 1) Investigators should promptly, completely, and correctly record data in the CRF based on the original observation;
- 2) The PIs and the study coordinator will monitor if the study is carried out according to the protocol. The completed CRFs, after signed by the PIs, will be sent to the investigator who is responsible for data management;
- 3) Data input will be performed by an investigator and checked out by another independent investigator. CRFs will be stored in sequential order;
- 4) Data management can be inspected by the Clinical Research Ethics Committee of both Yale University and Central South University at any time.

## **13. Statistical analysis**

### **13.1 General principles**

- 1) Numeric variables will be presented as mean (standard deviation) or median (minimum, maximum; or interquartile range). Categorical variables will be presented as number of cases (percentage);
- 2) Two-tailed tests will be used in all statistical analysis, and a p value of less than 0.05 will be considered to be of statistical significance for the primary outcome. The Benjamini-Hochberge procedure will be applied to control for the multiple testing for all secondary outcomes.

### **13.2 Patient recruitment and drop-out status**

The status of patient recruitment and drop-out will be summarized and listed. Comparison of the overall drop-out rate between the two groups will be performed with chi-square test.

### **13.3 Patient populations used for analysis**

- 1) The modified intention-to-treat (ITT) population: The modified ITT population includes all patients who undergo randomization, surgery (as long as the skin incision is made), and have the primary outcomes data collected. Patients whose surgery is cancelled or aborted in the middle of surgery (after skin incision) will be included in this population.

The primary outcome is regarded as not collected in the following situations:

- a) death (within postoperative 5 days);
  - b) early hospital discharge (for non-medical reasons and within postoperative 5 days);
  - c) intubated/sedated/comatose for more than 24 hours (within postoperative 5 days);
  - d) withdraw consent (within postoperative 5 days);
  - e) data missing.
- 2) The per-protocol population: The patients from the modified ITT population will be included in the per-protocol population if they fulfill the eligibility, intervention, and outcome assessment specified by the protocol.

The following patients are excluded:

- a) ineligible patients
  - b) randomization allocation error;
  - c) SedLine monitor malfunction (not working at all or >50% of the anesthetic duration (PSI <75) without monitoring data);
  - d) SedLine monitor not blinded in the usual care group;
  - e) being anesthetized with inhalational anesthetics;
  - f) surgery aborted or converted to open.
- 3) As-treated population from the SedLine-guided care group: This population is a subset of the per-protocol population. For patients from the SedLine-guided care group, they are regarded as fulfilling the as-treated criteria if the below-10 SEF AUC (left + right) is less than 10 (or the median value of the AUC, if AUC < 10 gives less than 300 patients). These patients are regarded as having received effective SedLine-guided intervention. This rule does not apply to patients from the per-protocol population from the usual care group.

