### **Evaluation of secondary endpoints**

- 1) Non-normal continuous endpoints will be analyzed by the Wilcoxon rank sum test. The Hodge-Lehman method will be used to estimate median of between-group difference with 95% CI.
- 2) Time-to-event variables (length of ICU stay, length of hospital stay) will be analyzed by the Wilcoxon rank sum test or by survival analysis, with difference between groups assessed with Log-Rank test.
- 3) The incidence of postoperative complications and 30-day mortality will be compared with Chi-square test or Fisher's exact test as appropriate.

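### If analysed in any set the plan defines, 30-day mortality, ICU admission and the complication composite would omit patients who die, or are intubated, sedated or comatose for more than 24 hours, within 5 days

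*Combined protocol and SAP*

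**What the plan says.** Section 13.3 lists the populations to be used for analysis. There are three.

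- **Modified ITT.** "The modified ITT population includes all patients who undergo randomization, surgery (as long as the skin incision is made), and have the primary outcomes data" (that is, on record). The section continues: "The primary outcome is regarded as not collected in the following situations". Five situations follow, among them a) "death (within postoperative 5 days" and c) "intubated/sedated/comatose for more than 24 hours (within postoperative 5 days". The others are non-medical discharge within 5 days, withdrawal of consent within 5 days, and missing data.
- **Per-protocol.** "The patients from the modified ITT population will be included in the per-protocol population", subject to further conditions.
- **As-treated.** Defined as a subset of the per-protocol set.

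Section 8.2 lists "30-day all-cause mortality", ICU admission and a 30-day composite of Clavien-Dindo grade II or greater as secondary outcomes. In the grading table there, death is grade V and a life-threatening complication needing intermediate or intensive care is grade IV.

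Section 13.5, under the evaluation of secondary endpoints, says: "The incidence of postoperative complications and 30-day mortality will be compared with Chi-square test or Fisher's exact test as appropriate". That gives the test but no population. The sensitivity and subgroup paragraphs refer to an ITT dataset, which is not defined separately.

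**The concern.** Death and prolonged intubation or coma are used as reasons for leaving the analysis set. They are also secondary outcomes, or closely tied to them. A patient who dies on day 3 belongs to no defined set in which that death could count toward 30-day mortality. A patient ventilated for two days belongs to no defined set in which the ICU admission or a grade IV complication could count.

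None of these outcomes needs a delirium assessment. Section 2 makes in-hospital complications and 30-day mortality the trial's second purpose. On the defined sets, that purpose would be answered only among patients who survived and were assessable to day 5. The selection happens after randomisation and depends on the outcome, so randomisation no longer protects the comparison. If nobody names a set beforehand, the denominator for mortality can be chosen once the data are known.

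**Working it through.** **1. Membership, by tracing the definitions (Section 13.3).**

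- Death by day 5: primary outcome not collected, so not in modified ITT.
- Per-protocol is drawn from modified ITT, so the patient is not in per-protocol.
- As-treated is a subset of per-protocol, so the patient is not in as-treated.
- The same chain holds for more than 24 hours intubated, sedated or comatose within 5 days.
- Section 13 defines no full or safety set.

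**2. What stays in.** Deaths on days 6-30 in otherwise included patients are counted. So are ICU admissions without more than 24 hours of intubation, sedation or coma.

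**3. Are the data available?** Yes for operated patients. Section 7.3 follows complications and mortality to 30 days, the study flow chart has a day-30 visit, and the discharge form records survival and readmission at 30 days.

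**4. The denominator.** Section 4.2 gives 742 per group, from 14% versus 14% × 2/3 = 9.33%, two-sided 0.05, 80% power. The pooled two-proportion formula reproduces it:

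n = [1.960 × √(2 × 0.1167 × 0.8833) + 0.842 × √(0.14 × 0.86 + 0.0933 × 0.9067)]² / 0.0467² = 742.

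Then 742 × 1.05 = 779.1, close to the planned 780. The 5% is an allowance for loss to follow-up in sizing the primary comparison. It does not address this point.

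**5. Size for mortality (assumed rates; the documents give none).** With 30-day mortality m and share s of deaths by day 5, deaths per arm D = 780m, deaths lost e = D × s, reported rate = (D − e)/(780 − e).

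| m | D | e at s = 20% / 40% / 60% | reported rate |
|---|---|---|---|
| 0.5% | 3.9 | 0.8 / 1.6 / 2.3 | 0.40% / 0.30% / 0.20% |
| 1% | 7.8 | 1.6 / 3.1 / 4.7 | 0.80% / 0.60% / 0.40% |
| 2% | 15.6 | 3.1 / 6.2 / 9.4 | 1.61% / 1.21% / 0.81% |

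**6. Size for ICU admission (assumed).** Take 5% admitted, and v = 0.5-2% of all patients intubated, sedated or comatose for more than 24 hours, all of them in the ICU. The reported rate is (0.05 − v)/(1 − v), which falls from 4.5% at v = 0.5% to 3.1% at v = 2%.

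**7. Effect on a comparison (invented counts).** Deaths of 12/780 versus 3/780 give Fisher p = 0.034, before the multiplicity adjustment of Section 13.1. If 9 of the 12 fall by day 5 they leave the set, and the comparison becomes 3/771 versus 3/780, p = 1.00. The reverse pattern could create a difference.

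**The case against.** The strongest reply is that Section 13.5 assigns the secondary outcomes to no set, so nothing in the plan says early deaths are left out. A reader might infer a stated rule that no death in days 0-5 may be counted. The text does not go that far. What stands is conditional: the events are lost if any defined set is used, and there is no other set to use.

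A second reply is that the plan elsewhere suggests wider retention. Section 3.3 excludes patients who remain intubated from the per-protocol analysis only, follows converted patients for intention-to-treat, and carries the last recorded result forward for drop-outs. This may show intent, but it conflicts with situation c) in 13.3 and does not cure it. The undefined ITT dataset does not help either. It is probably shorthand for the modified ITT, and it is used only for the primary-outcome sensitivity analysis and the subgroups.

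A third reply is that early deaths would not disappear from the trial. That is right. Section 13.2 summarises drop-outs by arm, Section 3.3 records reasons, and Section 10.3 requires severe adverse events to be reported within 24 hours. None of these is a between-arm analysis of mortality.

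Finally, numbers are likely to be small. Patients are elective, ASA I-III, with extubation expected, and those unlikely to survive 5 days are excluded. This limits the size. With outcomes this rare, though, a few cases can decide the result.

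**Conclusion.** The concern holds in conditional form. The only defined sets exclude early deaths and prolonged intubation, sedation or coma, and no set is named for the outcomes that these events make up. Under 30-day mortality of 0.5-1% with 20-40% of deaths by day 5, about 1-3 deaths per arm would be lost. The true figure is unknown because the documents give no rates.

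Two further inferences are not supported.

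- A reader might infer that all removed patients carry the gravest grade. Non-medical discharge, withdrawal and missing data imply no severity, and situation c) includes sedation, which need not be a grade IV complication.
- A reader might infer that the set should start at induction, because guided care begins there (Section 6.4). But outcomes are timed from surgery, and the documents show no 30-day follow-up for patients cancelled before incision.

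This should be fixed. It stops short of essential because the affected outcomes are secondary and the primary analysis is unchanged.

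**What to change.** Add to 13.3 a full analysis set: all randomised patients with a skin incision, analysed by assigned arm, whether or not the delirium outcome was collected, using data up to any withdrawal of consent. In 13.5, name it for 30-day mortality, complications including the Clavien-Dindo composite, ICU admission, 30-day readmission and adverse events. Keep the delirium-data condition for the delirium outcome only.

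Reconcile Section 3.3 item 6 with situation c) in 13.3, and say which set the ITT dataset means in the sensitivity and subgroup paragraphs.

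Emergence delirium and length of stay should not simply be moved into this set. The first needs an extubated patient who can be assessed (Section 7.3 and the CAM-ICU worksheet). The second needs a rule for death.

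The cost is SAP wording. No new data are needed and the sample size does not change. The small downside is that primary and secondary tables will have different denominators.
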